74. Alcorn JL, 3rd, Strickland JC, Lile JA, Stoops WV, Rush CR. Acute methylphenidate administration reduces cocaine-cue attentional bias. *Prog Neuropsychopharmacol Biol Psychiatry*. 2020;103:109974.

Objectives

List your research objectives. Please include a summary of intended research objectives in the box below.

Before the study proper, we will conduct a pilot study to validate our attentional bias task in healthy controls who may or may not have a history of current or active smoking. The specific aim of this pilot would be to show differences in attentional bias between smokers and non smokers.

Study proper. Specific Aim 1 will demonstrate whether one session of MRI targeted TBS to left dorsolateral prefrontal cortex (DLPFC) will decrease attentional bias to smoking cues, compared to sham TMS. Subjects will receive both one TBS session (1800 pulses) and one session of sham TMS, lasting 10 minutes on separate days. They will perform an attentional bias task before and after TBS. We hypothesize that TBS will significantly decrease post session attentional bias to smoking cues compared to sham TMS.

Specific Aim 2 will demonstrate whether one session of TBS versus sham TMS, to left DLPFC can modulate stress induced craving for smoking. Subjects will perform the short form of tobacco craving questionnaire (TCQ-SF) before and after TBS. We hypothesize TBS will significantly decrease craving in smoking patients compared to sham TMS.

Specific Aim 3 will demonstrate whether one session of TBS versus sham TMS, to left DLPFC can increase seed based functional connectivity (fc) in the ventral striatum. We will acquire resting state functional MRI (fMRI) scans before and after TBS in all subjects. We hypothesize increase in fc in the dorsal anterior cingulate – ventral striatum circuit after TBS.

Study Design

Describe and explain the study design (e.g., observational, secondary analysis, single/double blind, parallel, crossover, deception, etc.).

- **Clinical Research:** Indicate whether subjects will be randomized and whether subjects will receive any placebo.
- **Community-Based Participatory Research:** If you are conducting community-based participatory research (CBPR), describe strategies for involvement of community members in the design and implementation of the study, and dissemination of results from the study.
- **Qualitative research:** Indicate ranges where flexibility is needed, if a fixed interview transcript is not available, describe interview topics including the most sensitive potential questions.
- **Research Repositories:** If the purpose of this submission is to establish a Research Repository (bank, registry) and the material you plan to collect is already available from a commercial supplier, clinical lab, or established IRB approved research repository, provide scientific justification for establishing an additional repository collecting duplicate material. Describe the repository design and operating procedures. For relevant information to include, see the UK Research Biospecimen Bank Guidance or the UK Research Registry Guidance.

Before the actual study, we will conduct a pilot study involving 30 healthy controls who may or may not have a history of current or active smoking. They will perform the attentional bias task that we plan to use in the study proper. This would be an open label study, each subject would perform two versions of the attentional bias task lasting close to a total of 30 minutes.

Study Proper. This will be a double blind randomized controlled trial. All subjects will receive both TBS and sham TMS in a randomized manner with counter balancing. The TBS session and sham TMS will be done on separate days. Subjects will be randomized to receive either TBS first and sham TMS second, or sham TMS first and TBS second. The PI ([name]) will be blind to the randomization status and will supervise the TMS session. Subjects will also remain blind to the randomization status. This will be facilitated by the Magventure Active/sham TMS coil which has been shown to maintain integrity of blinding in subjects regarding group assignment. We will recruit 30 patients from one of these clinics - the Bluegrass Clinic, SMART clinic in psychiatry and Beyond Birth Clinic in Psychiatry. All of them would receive TBS and sham TMS on separate days. The Bluegrass HIV clinic has a closely monitored population of PLWHA patients. The PI ([name]) and a research assistant would interface with [name] at the Bluegrass HIV Clinic on a weekly basis and with [name] on a daily basis to recruit patients for this study. The PI ([name]) and the research assistant will also interface with [name] (who heads the SMART clinic and Beyond Birth Clinic) on a weekly basis. If interested in participating, we will provide subjects with information and seek informed consent before proceeding with the study.

A sequential timeline of assessments and interventions are shown in table one. After informed consent, subjects will get an MRI brain scan at the Magnetic Resonance Imaging and Spectroscopy Center (MRISC) affiliated with University of Kentucky. Subjects will also be escorted to the MRISC at the UK Medical Center by the PI ([name]) and a research assistant. Subsequently, neuroimaging data (MRI brain) will be acquired using a Siemens 3-Tesla (3T) PRISMA MRI scanner as described under Data Collection below. This will happen on day 1. Then, on days 2 and 3, subjects will be scheduled for three hour experimental sessions at the TMS Suite at [name]. During these three hour sessions, subjects will perform the tobacco craving questionnaire (TCQ) while performing stress induced craving paradigm, attentional bias task and delayed discounting task. These activities will last an hour. Then we will obtain active motor threshold (AMT) from the first dorsal interosseous (FDI) muscle and left motor cortex, following which we will administer either a session of theta burst stimulation (TBS) for 9 minutes at 80% active motor threshold (AMT) or sham TMS to the left dorsolateral prefrontal cortex using a figure 8 coil and MagVenture MagPro x100 device (MagVenture A/S, Denmark), with TMS coil position stabilized using BrainSight (Rogue Solutions, Montreal, Canada). We will record motor evoked potential before and after the TBS session to assess response (10% increase in MEP to be a cutoff parameter). These activities will last another hour. After the TBS/sham TMS session, subjects will perform TCQ concomitant with the stress induced craving paradigm, attentional bias and delayed discounting tasks. These will last an hour. Then subjects will be transported to MRISC for their post TBS session MRI brain scan in the 3-Tesla (3T) PRISMA scanner.

Table 1

Study Task Study Day Pre- TBS Post-TBS

Urine Pregnancy Test 1

MRI brain at MRISC (Pre-TBS) 1

Exhaled CO 2 and 3 X

Motor Threshold 2 and 3 X

Eye tracking to measure AB 2 and 3 X X

Delayed Discounting Task 2 and 3 X X

Tobacco Craving Questionnaire 2 and 3 X X

TMS Side Effects Questionnaire 2 and 3 X

Treatment Acceptability Questionnaire 2 and 3 X

MRI brain at MRISC (Post-TBS) 2 and 3 X

Attachments

Subject Recruitment Methods & Advertising

Describe how the study team will identify and recruit subjects. Please consider the following items and provide additional information as needed so that the IRB can follow each step of the recruitment process.

- How will the study team identify potential participants?
- Who will first contact the potential subjects, and how?
- Will you use advertisements? If so, how will you distribute those?

- How and where will the research team meet with potential participants?
- If applicable, describe proposed outreach programs for recruiting women, minorities, or disparate populations?
- How you will minimize undue influence in recruitment?
- Attach copies of all recruiting and advertising materials (emails, verbal scripts, flyers, posts, messages, etc.).

For additional information on recruiting and advertising:

- [IRB Application Instructions - Advertisements](#)
- [PI Guide to Identification and Recruitment of Human Subjects for Research](#)

For the pilot study, we will recruit 30 healthy volunteer subjects from in and around [name] to perform the computer based attentional bias task. This would essentially comprise office staff and other employees in [name]. There will be no coercion and subjects can individually choose if they would like to participate in this pilot study. Each subject would be administered two versions of the task for a total of approximately 30 minutes.

For the study proper, we will recruit 30 subjects from the Bluegrass HIV Clinic, SMART clinic and Beyond Birth Clinic. Study members will interface with all providers in these clinics on a daily basis. All providers in these clinics will be provided multiple copies of the study flyer. All providers in these clinics will also be informed about inclusion and exclusion criteria for the study, based on which all patients will be screened by them. The PI ([name]) and a research assistant will interface with a contact in each of these clinics on a daily basis. Business cards (that list a few study details and a call back number if subjects are interested in the study) will be provided to subjects at each of these clinics by clinic providers. The case manager for this clinic [name] will send an email to all patients from the clinic, with the study flyer attached and informing them about the study. Subjects interested in the study can call the number provided on the business card to express interest in the study. This number belongs to the PI ([name]). He or the research assistant will administer a phone script to subjects who call back to assess subjects' suitability for the study. Once a subject is identified as suitable for the study, they will be asked to meet [name]/research assistant at [name] to get informed consent if they are interested in study participation and fulfill other eligibility criteria for the study. This process will also encompass MRI screening, examining urine drug screen and breathalyzer results. Following this step, patients will be randomized to either the treatment arm or sham arm by study co-investigator [name]. Half of compensation for study participation would be provided prior to starting the study and rest of it at study completion. All data collected from phone screening would be entered into RedCap, regardless of whether subjects do or don't fulfill inclusion and exclusion criteria.

Pertaining to the modification of study design - For subjects who have already participated in our trial and received one TMS session, we will inform them about this modification and ask them if they would be interested in coming back to receive another session of TMS (which may be active or sham, they will receive the opposite of what they got initially). The randomization procedure will be supervised by [name] this will be factored into the randomization counterbalancing procedure. We will educate participants who have completed the study previously on the modification of study design and offer them the modified consent form to read and sign if they are interested in participating in the third day of the study.

No flyers will be created for the pilot study. For the main study, we will create study flyers for providers at three clinics. These will list inclusion and exclusion criteria for the study as well as contact numbers for the PI ([name]) and research assistant involved in the study.

Attachments

Attach Type	File Name
Advertising	64473_business_card PR edit STAMPED.pdf
Advertising	Bell_email.docx
Advertising	Rakesh_Flyer PR STAMPED.pdf

Research Procedures

Describe how the research will be conducted.

- What experience will study participants have?
- What will study participants be expected to do?
- How long will the study last?
- Outline the schedule and timing of study procedures.
- Provide visit-by-visit listing of all procedures that will take place.
- Identify all procedures that will be carried out with each group of participants.
- Describe deception and debrief procedures if deception is involved.

Differentiate between procedures that involve standard/routine clinical care and those that will be performed specifically for this research project. List medications that are explicitly forbidden or permitted during study participation.

Before the study proper, we will run a pilot to validate the attentional bias task. In this pilot, 20 subjects with current or previous history of smoking as well as 20 subjects with no history of current or previous smoking will perform a computerized behavioral task that examines attentional bias to smoking cues versus neutral cues. Subjects will perform the attentional bias task following informed consent. Following informed consent, they will undergo breathalyzer and CO estimation prior to the study session.

Study Proper

Following informed consent, the subject will be asked to come to MRISC for a MRI brain scan contingent on the investigative team obtaining a slot for this. The PI will coordinate with staff at MRISC to obtain a MRI slot. Subjects will also be escorted to the MRISC at the UK Medical Center by the PI ([name]) and a research assistant. Neuroimaging data (MRI brain) will be acquired using a Siemens 3-Tesla (3T) PRISMA scanner as described under Data Collection below. This will happen on day 1 and will last an hour. Then, on days 2 and 3, subjects will be scheduled for three hour experimental sessions at the TMS Suite at [name]. During these three hour sessions, subjects will perform the tobacco craving questionnaire (TCQ) while performing stress induced craving paradigm, attentional bias task and delayed discounting task. These activities will last an hour. Then we will obtain active motor threshold (AMT) from the first dorsal interosseous (FDI) muscle and left motor cortex, following which we will administer either a session of theta burst stimulation (TBS) for 9 minutes at 80% active motor threshold (AMT) or sham TMS to the left dorsolateral prefrontal cortex using a figure 8 coil and MagVenture MagPro x100 device (MagVenture A/S, Denmark), with TMS coil position stabilized using BrainSight (Rogue Solutions, Montreal, Canada). We will record motor evoked potential before and after the TBS session to assess response (10% increase in MEP to be a cutoff parameter). These activities will last another hour. After the TBS/sham TMS session, subjects will perform TCQ concomitant with the stress induced craving paradigm, attentional bias and delayed discounting tasks. These will last an hour. Then subjects will be transported to MRISC for their post TBS session MRI brain scan in the 3-Tesla (3T) PRISMA scanner.

Motor Threshold

Motor threshold (MT) is defined as the TMS pulse amplitude needed to elicit an EMG response of 50 μ V peak-to-peak average amplitude in a target muscle. MT is the standard in the field for determining the intensity of TMS for everyone to reduce seizure risk. The MEP for the right first dorsal interosseous (FDI) will be measured with EMG. The scalp region producing the largest amplitude MEP will be identified. At that scalp location, we will determine the TMS intensity eliciting average MEP amplitude of 50 μ V peak-to- peak in the first DI muscle using an amplitude titration procedure (at least 5/10 trials). Individual MT will be used to determine the intensity of theta burst stimulation for everyone, as recommended by safety guidelines.

TBS application

A magnetic coil will be placed on the scalp and held in place with frameless stereotaxic equipment, using a sophisticated method of coil placement that will coregister scalp positions directly onto an average brain template. This Frameless Stereotaxic System Brainsight offers real-time three-dimensional display of cortical localization as the TMS coil is moved across the scalp. This will be used for coil positioning. This system uses a programmed robot arm to precisely position the TMS coil, and maintain its position, within 1 mm of the brain target chosen. Earplugs will be worn to protect hearing and low-volume white noise will be played through TMS-compatible headphones to mask the sound of the coil clicks. The intensity of the stimulation will be 120% of resting motor threshold as reported in a previous studies. The participant will be seated comfortably with headphones and earplugs to protect the subject's hearing. Before applying TBS or sham TMS, we provide subjects without scalp hair the option to apply 5% lidocaine spray (aspercreme) that is available over the counter to the left frontal quadrant of their scalp. This would minimize discomfort if any they feel during the stimulation. They would have the option to refuse as well.

Stress induced craving paradigm

The pathophysiology of nicotine dependence includes the interaction between stress, environment and body physiology. Multiple previous studies have modeled craving for nicotine in the presence of stress, to approximate real world scenarios. Before we test TBS as a clinical intervention, we will explore whether one session of TBS can modulate craving in the context of induced stress. Two promising paradigms for stress induction are the cold pressor test (CPT) wherein participants immerse their feet in ice cold water (2-4 degree Celsius) for three minutes and the paced serial addition task (PASAT). The cold pressor test invokes an immediate cardiovascular stress response, initiated by the sympathetic nervous system, followed by a neuroendocrine response controlled by the hypothalamus-pituitary-adrenal (HPA) axis. The PASAT is a cognitively challenging task and will be performed in parallel with the CPT as an additional means for stress induction. The task requires participants to listen to a standardized audio-recording of a series of single-digit numbers and to say aloud the sum of the last two numbers presented (within each inter-trial interval). The PASAT will also last about three minutes. Peak stress response occurred 20 minutes after these paradigms were performed. In our pilot study, these paradigms will be performed simultaneously, and followed by the tobacco craving questionnaire (TCQ).

The Tobacco Craving Questionnaire-short form (TCQ-SF)

It consists of 12 items rated on a visual analogue scale. The original Tobacco Craving Questionnaire (TCQ) is a valid and reliable 47-item self-report instrument that assesses tobacco craving in four dimensions: emotionality, expectancy, compulsivity, and purposefulness. The short form has been found to be as valid and reliable as the original version.

Attentional Bias task

We will measure attentional bias using a validated database of smoking and neutral cues and Tobii Pro Fusion 120 Hz eye tracker (Tobii Technology, Sweden). Smoking and neutral cues will be presented side-by-side on the screen for 1000?milliseconds. Eye tracking will record eye movements and fixation times for both cue types. Upon offset of the cues, a visual probe ('X') will appear on either the left or right side of the computer screen. Participants will be instructed to respond as quickly as possible to the probe. The primary dependent variable will be mean fixation time (milliseconds) calculated by summing the total fixation time for each cue type and then dividing by the total number of critical trials (i.e., 40). Reaction times to the visual probe will also be collected.

Attention bias behavioral activation (ABBA) task using go/no go

A modified cued go/no-go task is used as a measure of inhibitory control. The procedures and parameters for the attentional bias-behavioral activation (ABBA) task are identical to the traditional cued go/no-go task except that opiate-related images serve as go cues and neutral images serve as no-go cues. Opiate related images and neutral images that will be used for this task are attached below.

Delayed discounting task

Participants are presented a fixed set of 27 choices between smaller, immediate rewards (SIRs) and larger, delayed rewards (LDRs). Three trials of the task are presented, money versus money, money versus opiate reward, and opiate versus opiate reward in varying amounts and with varying time periods. The 27 choices in each of these trial types define ten ranges of discount rates, eight of which are bounded above and below and two of which represent the endpoints (choices of all 27 immediate rewards or all 27 delayed rewards). Based on participants' choices of the immediate reward across trials, each participant is assigned a k value corresponding to the geometric midpoint of one of the eight ranges or one of the two endpoint values. Each participant is assigned a k value that yields the highest proportion of choices consistent with that assignment. That is, for each participant we compute the proportion of that person's choices that were consistent with assignment to each of the 10 values of k defined by the questionnaire (bounded or unbounded), and the participant is assigned to the value that yields the highest consistency among his or her choices. The discount rate that yields the highest relative consistency across trials provides the best estimate of the participant's k value. When two or more values yielded equal consistency, the participant is assigned a value corresponding to the geometric mean of those values. The discounting rate (k) is estimated with nonlinear regression using Mazur's (1987) hyperbolic-decay model, $vd = V/(1+kd)$, where V is the value of a an outcome delayed by d days and vd is the value of the immediate outcome – a proportion of V subjectively discounted at "rate" k. Distributions of k-values transformed with the natural logarithm (ln) tend to be approximately normal.

Barratt impulsiveness scale (BIS-11) - The BIS-11 is a 30-item self-report questionnaire to assess impulsivity that has been validated in multiple studies and other languages.

Attachments

Attach Type	File Name
ResearchProcedures	COC.pdf

Data Collection & Research Materials

In this section, please provide the following:

- Describe all sources or methods for obtaining research materials about or from living individuals (such as specimens, records, surveys, interviews, participant observation, etc.), and explain why this information is needed to conduct the study.
- For each source or method described, please list or attach all data to be collected (such as genetic information, interview scripts, survey tools, data collection forms for existing data, etc.).
- If you will conduct a record or chart review, list the beginning and end dates of the records you will view.

Motor Threshold

Eye tracking

Delay discounting task

Attention bias behavioral activation (ABBA) task using go/no go

Barratt impulsiveness scale (BIS-11)

Tobacco Craving questionnaire (TCQ)

TMS Side effects scale

Treatment acceptability questionnaire (TAQ)

Resting state functional magnetic resonance imaging (fMRI)

Neuroimaging data will be acquired on a Siemens 3-Tesla (3T) PRISMA scanner. A high-resolution (1 cubic millimeter voxels) T1-weighted MP-RAGE structural image will be acquired for each subject. Functional images will be acquired using echo-planar imaging. Hyper-angulated volumes will be acquired with 37 ascending and interleaved slices at an angle 30-degrees to the anterior-posterior commissure to prevent OFC washout. Additional parameters will be similar to those used in other approved neuroimaging protocols in our lab (e.g., a repetition time (TR) of 2 seconds, echo time (TE) of 25 ms, a flip angle of 90 degrees, and functional voxels of size 3.4mm x 3.4mm x 4.0mm). Image preprocessing will be performed in statistical parametric mapping (SPM) 12 software using standard procedures (see Wesley et al., 2014). Data from functional scans will be treated similarly to fMRI data in previous studies

(e.g., slice-timing corrected, head-motion corrected, warped into MNI standard space, re-sliced to 4 cubic millimeter smoothed with an 8mm full-width, half-maximum (FWHM) Gaussian kernel).

Attachments

Attach Type	File Name
DataCollection	PreScrnF.pdf
DataCollection	Attentional_Bias_Behavioral_Activation.pdf
DataCollection	BIS.pdf
DataCollection	Stress paradigms.pdf
DataCollection	TCQ-SF.png
DataCollection	TMS_Side effects.doc
DataCollection	TAQ.PNG
DataCollection	Delayed_discounting choices.docx

Resources

Describe the availability of the resources and adequacy of the facilities that you will use to perform the research. Such resources may include:

- Staffing and personnel, in terms of availability, number, expertise, and experience;
- Computer or other technological resources, mobile or otherwise, required or created during the conduct of the research;

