Theta burst stimulation (TBS). A new TMS paradigm, theta burst stimulation (TBS), uses theta frequency stimulation at gamma frequency. TBS is different from other TMS frequencies in that it delivers significantly more dosing pulses over the same time period. TBS is safe and was approved for MDD by the FDA in 2019. To the best of our knowledge, there has been only a single clinical study that utilized theta burst stimulation for smoking cessation. Four sessions of intermittent TBS (iTBS) added to Cognitive Behavioral Therapy (CBT, twice weekly sessions for three weeks) (56) were delivered. Participants (N=74) received either iTBS (600 pulses) or sham TMS. The groups did not differ in number of cigarettes smoked or scores on Fagerstrom Test for Nicotine Dependence (FTND). At three months of follow-up, the iTBS group had 19 subjects reporting abstinence while 19 had relapsed. The sham TMS group had 10 subjects abstinent and 26 subjects who had relapsed. To the best of our knowledge, no studies used TBS or other rTMS for smoking cessation in PLWHA.

TMS for modulation of cognitive performance including attentional bias. TMS has also been used to modulate cognitive performance, to accelerate mechanisms of smoking cessation across various studies (57, 58). Previous TMS treatment studies for smoking cessation have included cognitive outcome measures including delayed discounting (59, 60) and cigarette cue induced craving assessed using an analogue scale (61). It is plausible modulation of these cognitive paradigms by TMS could contribute to craving reduction and behavioral changes in cigarette use. Multiple previous studies support the existence of an attentional bias towards smoking related cues compared to neutral cues in tobacco use disorder(62). Modulation of attentional bias has been attempted in MDD. To the best of our knowledge, no study has used TMS to modulate attentional bias in subjects with smoking behavior.

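### The crossover states no minimum interval between TBS and sham, and Aim 3, with its only pre-stimulation scan on Day 1, has no protection against TBS effects carried into the sham session

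*Combined protocol and SAP*

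**What the plan says.** The Study Design section describes a two-sequence crossover: "Subjects will be randomized to receive either TBS first and sham TMS second, or sham TMS first and TBS second". It plans 30 patients, each receiving both conditions. On spacing it says only that "The TBS session and sham TMS will be done on separate days". The Aim 1 text under Objectives has the same rule. Study Design and Research Procedures add visit labels: "on days 2 and 3, subjects will be scheduled for three hour experimental sessions". The text available gives no washout, no minimum or maximum gap, and no reason for the gap.

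Subject Recruitment Methods & Advertising explains that the crossover was introduced by modification. Subjects who had already received one session are invited back for the opposite condition, again with no interval stated.

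Table 1 schedules the measurements differently by aim:

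- Attentional bias and the craving questionnaire are taken before and after stimulation on both Day 2 and Day 3.
- The MRI rows read "MRI brain at MRISC (Pre-TBS) 1" and "MRI brain at MRISC (Post-TBS) 2 and 3 X". There is one pre-stimulation scan, and the Day 3 session has no pre-scan of its own.

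The analysis text at the end of the document contrasts baseline, post-iTBS and post-sham connectivity within subject. It uses linear fixed effects regressions for attentional bias and craving. It names no period, sequence or carry-over term for any aim.

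**The concern.** A crossover estimate is unbiased for the treatment effect only if the first treatment's effect has gone by the second period, or if the analysis can remove what is left. Here the schedule allows the sham session on the day after TBS, and the plan neither states nor supports the assumption that nothing is left by then.

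For Aims 1 and 2, a pre-session score taken on the same day can absorb a residue. For Aim 3 nothing can: a subject who gets TBS first has the sham scan taken on top of whatever TBS effect remains, and the planned contrast counts that residue as sham response. A weak or null connectivity result would then be hard to interpret. This matters because the background section says the data will support a grant resubmission.

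**Working it through.** The documents give no power, SD or alpha for the 30 subjects, so there is no stated figure to reproduce. The check has three steps.

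**1. Does the Day 1 baseline protect Aim 3?** Let b be the baseline, d the true TBS effect on the post-session scan, and L the share of d still present at the other session when TBS came first.

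- TBS first: the TBS scan is b + d and the sham scan is b + L·d. The contrast is d(1 - L).
- Sham first: the sham scan is b and the TBS scan is b + d. The contrast is d.

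Subtracting the Day 1 scan from both terms changes nothing: (TBS - b) - (sham - b) = TBS - sham. The shared baseline cancels. With half the subjects in each order (assumed from the counterbalancing), the mean is 0.5·d(1 - L) + 0.5·d = **d(1 - L/2)**. Balancing the orders halves the loss but does not remove it, because only TBS-first subjects can carry TBS into the sham scan.

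For Aims 1 and 2, the Day 3 pre-session score also contains L·d. Post minus pre then removes it, provided the residue is the same before and after the sham session.

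**2. How large is it?** Assumptions: n = 30, paired t-test, two-sided alpha 0.05, one outcome, L from 0 to 1. The effect sizes are illustrative. The second, 0.471, is the craving meta-analysis figure in the background and is not an Aim 3 value.

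| L | Contrast kept, 1 - L/2 | Power at 0.5 SD | Power at 0.471 SD |
|---|---|---|---|
| 0 | 100% | 75% | 70% |
| 0.25 | 87.5% | 64% | 59% |
| 0.5 | 75% | 51% | 46% |
| 1 | 50% | 26% | 24% |

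A simulation (20,000 runs per setting, within-subject correlation 0.3, 0.5 and 0.7) gave the same shrinkage: ratios of about 0.87, 0.75 and 0.50 at L = 0.25, 0.5 and 1.

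**3. Could the data reveal or avoid it?** Take 15 subjects per order, effect 0.5 SD and within-subject correlation 0.5. A within-subject difference then has SD √(2 × (1 - 0.5)) = 1.

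- *Day 3 pre-session scores compared by order.* The expected difference is L × 0.5 = 0.125, 0.25 or 0.5 SD at L = 0.25, 0.5 or 1. Power is 6%, 10% or 26%.
- *A between-order carry-over test on the scans* (effect 0.471, simulated). It detects L = 1 about 10-15% of the time and L = 0.5 about 6-8%, against a 5% false-positive rate.
- *Day 2 scan minus Day 1 scan, TBS-first versus sham-first.* This is free of carry-over, because nothing precedes Day 2. Its standard error is √(1/15 + 1/15) = 0.365, against 1/√30 = 0.183 for the crossover, so it is half as precise. Power at 0.5 SD is 26%.

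The Day 2-only estimate is therefore useful because it is unbiased. It is no more powerful than the crossover, even under full carry-over.

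**The case against.** The strongest reply is that the documents contain no evidence that one session's effect lasts overnight, so L may be zero. That stands. A reader might infer persistence from the trial described in the background, where "At three months of follow-up, the iTBS group had 19 subjects reporting abstinence while 19 had relapsed", against 10 abstinent and 26 relapsed on sham (19/38 = 50% versus 10/36 = 28%). The inference is not supported. Those patients had four sessions added to twice-weekly cognitive behavioural therapy. Abstinence can sustain itself once reached, and the comparison is borderline (Fisher p = 0.06). It says nothing about the next-day effect of one session on connectivity.

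Other replies also have force:

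- **Days 2 and 3 may be visit labels.** The Payment section speaks of a second and third session, and recalled subjects cannot have had a one-day gap. So the plan permits consecutive days; it does not prescribe them. The recall route also means that gaps vary between subjects.
- **Aims 1 and 2 might seem equally biased.** The documents do not show this. Pre and post scores are scheduled on both days, and the analysis text does not say that post-session scores alone will be compared.
- **Carry-over might seem certain to shrink the estimate, with no way to see it.** Shrinkage requires a residue of the same sign as the effect, and Day 2 against Day 1 gives a carry-over-free comparison, though an imprecise one.
- **The power figures are not Aim 3 power.** The plan uses seed-to-voxel maps with cluster-level FDR. The continuing-review section also reports a total of 10 enrolled. At n = 10 the same calculation starts at 29% power without any carry-over, so carry-over would not then be the main limit.
- **The consent form and attached protocol are not shown.** Either could state the spacing, so its absence is established only for the text available.

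None of this supplies a spacing rule or a same-day Aim 3 baseline.

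**Conclusion.** The point holds for Aim 3, conditionally. The stated rule permits sham on the day after TBS, the single baseline cannot absorb a residue, and the analysis text has no term for period or order. The expected Aim 3 contrast is (1 - L/2) of the truth, which ranges from no loss at L = 0 to a loss of half at L = 1.

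This rests on equal numbers in the two orders, residue of the same sign as the effect, and a value of L that the documents do not give. The 1 - L/2 factor needs no effect size or alpha; the power figures do, and are illustrative only. The finding is that the no-carry-over assumption is unstated and unsupported. It is not that carry-over will occur.

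**What to change.** 1. **Spacing.** In Objectives, Study Design and Research Procedures, state a minimum interval between the two stimulation sessions, the same in both orders, that excludes consecutive days. The sponsor should set and justify its length. Record each subject's actual gap, including subjects recalled from the single-session design.
2. **Analysis text.** Add period and sequence terms. Always report an Aim 3 estimate from the Day 2 scan against the Day 1 baseline, compared by order, beside the crossover estimate, and note its low precision.
3. **Description.** Show Day 3 pre-session attentional bias and TCQ-SF by order, descriptively. With 6-26% power under the assumptions above, this comparison should not act as a test that triggers other analyses. Behavioural carry-over also need not track connectivity carry-over.

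The application is marked closed. If no further sessions will take place, report the actual gaps and order, state the no-carry-over assumption for Aim 3, and show the Day 2-only result.

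The cost is protocol wording and scheduling, with no extra visit, scan or patient. The downside is somewhat longer participation and possibly a few more subjects not returning for the last session.
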